4.3. Enrollment Target and Study Duration

The target is to enroll approximately 70 eligible subjects with 60 subjects to complete the study. Subjects will be stratified into two arms: 20 subjects that are full time spectacle wearers (observational arm), and 40 subjects that are current spherical soft contact lens wearers (interventional arm). Within each arm, subjects will be dichotomized into two groups via the Classification Questionnaire. Group 1: half of subjects will have been classified as symptomatic high digital device users. Group 2: half of subjects will be classified as having low digital device use and/or asymptomatic with digital device use

The table below provides details of subject enrollment.

Table 1: Subject Enrollment

| | Habitual Spectacle Wearers (observational arm) | | Habitual Contact Lens Wearers (interventional arm) | | Total |
|----------------------------------|---|--|---|--|-------|
| | Group 1: High use and Symptomatic | Group 2: Low use and/or Asymptomatic | Group 1: High use and Symptomatic | Group 2: Low use and/or Asymptomatic | |
| Randomized (as applicable) | 12 | 12 | 23 | 23 | 70 |
| Complete | 10 | 10 | 20 | 20 | 60 |

There will be 2 visits for the observational arm and 4 visits for the interventional arm. The study is anticipated to last 6 weeks and include a 2-week enrollment period.

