5. TEST ARTICLE ALLOCATION AND MASKING

5.1. Test Article Allocation

Dispensed contact lenses will be worn in a bilateral fashion. Randomization is applicable in this study only in the interventional arm. Study lens and Spectacle will be worn in a bilateral

and random fashion for a period of 1 week each among subjects in the interventional arm. Subjects will be randomly assigned to one of two sequences (Spectacle /ACUVUE OASYS 1-Day or ACUVUE OASYS 1-Day /Spectacle). Groups based on the Classification questionnaire will be used as strata in the randomization, with a 1: 1 ratio for Group 1 (high use and symptomatic) and Group 2 (low use and/or asymptomatic) subjects.

The test article assignment of subjects must be performed at the Initial Visit. The following must have occurred prior to test article assignment:

- Informed consent has been obtained
- Subject meets all the applicable inclusion/exclusion criteria
- Subject history and baseline information has been collected

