| 1.34 | Subjective Best Sphere Over Refraction | Perform subjective best sphere refraction over the study lenses and record the best corrected Snellen distance visual acuity to the nearest letter (OD, OS). |
| 1.35 | Lens Power Modification | Adjust the lens power if the subject's best sphere over-refraction is not plano. For each power modification, repeat steps (1.32-1.34). Up to one power modification is allowed. |
| 1.36 | Subject Reported Ocular Symptoms | Subjects will respond to a verbal open-ended symptoms questionnaire. |
| 1.37 | Subjective Lens Fit Assessment | Evaluate overall lens fit acceptance (acceptable or unacceptable) based on centration, movement and other fitting characteristics. An unacceptable fit is deemed by one of the following criteria: 
 • limbal exposure at primary gaze or with extreme eye movement • edge lift • excessive movement in primary and up gaze • insufficient movement in all three of the following conditions: primary gaze, up gaze, and Josephson push up 
Note: if lens fit is unacceptable subject will be discontinued from the study.
 |

| Visit 1: Treatment 1 (Study lens fitting) | | |
|---|--------------------------------------|--|
| Step | Procedure | Details |
| 1.38 | Contact Lens corrected Visual Acuity | Perform monocular distance and near ETDRS LogMAR visual acuity test, OD & OS |
| 1.39 | Exit Snellen Visual Acuity | Record the Snellen visual acuity, distance and near, OD & OS. Subjects must read the smallest line until at least 50% of the letters are read incorrectly. |
| 1.40 | Continuance | 
For the subject to continue in the study, they must meet all three of the following criteria:
 
 • Snellen visual acuity is 20/25 or better, distance and near (OD, OS) • The lens fit is acceptable OD and OS • Investigator approval 
If the Investigator does not approve the dispensing of the first study lens, then the study is terminated for that subject.
 |

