| 2.4. | Subject Reported Ocular Symptoms | Subjects will respond to a verbal open-ended symptoms questionnaire. | |
| 2.5. | Follow-Up Spectacle Questionnaires (if applicable): DEQ-5, MRD, and Digital Device | The subject will respond to the Follow-Up Questionnaire. | |
| 2.6. | Follow-Up Contact lens Questionnaires (if applicable): CLDEQ-8, MRD, and Digital Device | The subject will respond to the Follow-Up Questionnaire. | |
| 2.7. | Visual Acuity | Perform monocular distance and near ETDRS LogMAR visual acuity test, OD & OS | |
| 2.8. | Subjective Lens Fit | Evaluate overall lens fit acceptance | |

| Visit 2: Treatment 1 Follow-Up 1 | | |
|----------------------------------|--|--|
| Step | Procedure | Details |
| | Assessment (if applicable) | 
(acceptable or unacceptable) based on centration, movement and other fitting characteristics.
 
An unacceptable fit is deemed by one of the following criteria:
 
 • limbal exposure at primary gaze or with extreme eye movement • edge lift • excessive movement in primary and up gaze • insufficient movement in all three of the following conditions: primary gaze, up gaze, and Josephson push up 
Note: if lens fit is unacceptable subject will be discontinued from the study.
 |
| 2.9. | Wettability Characteristics (if applicable) | Record the white light lens wettability of both lenses. |
| 2.10. | Surface Debris & Deposits (if applicable) | Record any front and back surface lens debris & deposits. |
| 2.11. | Tear film stability (Pre-Lens or Pre-Corneal as applicable) | Record the first tear film stability (NIBUT/NIKBUT), OD & OS. Record three measurements. |
| 2.12. | Blink patterns (as site applicable) | Record the Blink Patterns, OD & OS |
| 2.13. | Pre-corneal or Pre-lens (as applicable) tear film lipid layer thickness as available by site | Record the tear film lipid layer thickness, OD & OS |
| 2.14. | Lens Removal and Storage (if applicable) | 
The lenses will be removed by the subject. VRC site only, both lenses will be stored dry in a labeled glass vial and frozen, using study specific labels.
 
Otherwise, lenses will be discarded.
 |
| 2.15. | Slit Lamp Biomicroscopy | FDA Slit Lamp Classification Scale will be used to grade the findings and determine eligibility. |

| Visit 2: Treatment 1 Follow-Up 1 | | | |
|----------------------------------|---|---|---|
| Step | Procedure | Details | |

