| | | If the subject has a Grade 3 slit lamp finding, it will be recorded as an Adverse Event | |
| 2.16. | Lid wiper Epitheliopathy | Record the lid wiper epitheliopathy (upper & lower) by Lissamine green, OD & OS | Lid Wiper Epitheliopathy Work Aid (Appendix H) |
| 2.17. | Conjunctival staining | Record the conjunctival staining by Lissamine green, OD & OS | |
| 2.18. | Meibomian Gland Expressibility (Lower lid, 3 regions) | Record the Meibomian Gland Expressibility, OD & OS via Meibomian Gland Secretion Grading Scale (Appendix I) | Procedure per Meibomian Gland Evaluator manufacturer instructions. (Appendix I) |
| 2.19. | Eye Rinse | If the clearance if dye needs to be expedited, the study investigator or technician will rinse the subject's eyes thoroughly with a study provided solution. | |
| 2.20. | Exit Visual Acuity (if applicable) | Record the Snellen distance visual acuity, OD & OS with habitual contact lenses or spectacles. Subjects must read the smallest line until at least 50% of the letters are read incorrectly. Record correction used. | |
| 2.21. | Subject Instruction | 
Subjects in the observational arm will complete the Exit Evaluation.
 
Subject in the interventional arm will continue in the study:
 
 Subjects in the interventional arm will be scheduled for Visit 3 following a one-week washout period in which they will wear their habitual lens per their habitual wear schedule, ensuring that they wear their habitual lens at least 6 hours on the day of the next visit. | |

WASHOUT (5-7 days): One-week washout period in which subjects will wear their habitual lens per their habitual wear schedule

VISIT 3

The subjects must present to Visit 3, 6-8 days following Visit 2. The subjects must present after at least 6 hours of habitual contact lens wear time on the day of the visit.

| Visit 3: Treatment 2 | | |
|----------------------|---|---|
| Step | Procedure | Details |
| 3.1. | Adverse Events and Concomitant Medications Review | Review any changes to the subject's medical history or concomitant medications from the previous study visit. Record any changes, and any adverse events. |
| 3.2. | Subject Reported Ocular Symptoms | Subjects will respond to a verbal open-ended symptoms questionnaire. |

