8.2. Withdrawal/Discontinuation from the Study

A subject will be withdrawn from the study for any of the following reasons:

- Subject death during the study period
- Subject withdrawal of consent
- Subject not compliant to protocol
- Subject lost to follow-up
- Subject no longer meets eligibility criteria (e.g. the subject becomes pregnant)
- Subject develops significant or serious adverse events causing discontinuation of study lens wear
- Subjects who have experienced a Corneal Infiltrative Event (CIE)
- Investigator's clinical judgment regarding the subject safety reasons (that it is in the best interest of the subject to stop treatment)
- Subject missed study visits
- Subject not compliant with study lens wear schedule
- Subject not successfully dispensed due to lack of efficacy and safety including poor vision, poor comfort or unacceptable fit

For discontinued subjects, the Investigator will:

- Complete the current visit (scheduled or unscheduled)
- Complete the Final Evaluation, indicating the reason that the subject was discontinued from the study
- Record the spherocylindrical refraction with best corrected distance visual acuity

- Collect used test article(s) (worn or brought to the visit) from the subject and discard them, unless otherwise stated in Section 7.2
- Collect all unused test article(s) from the subject

An additional subject will be enrolled if a subject discontinues from the study prematurely.

In cases where a subject is lost to follow-up, every possible effort must be made to contact the subject and determine the reason for discontinuation/withdrawal. The measures taken to follow up must be documented including two written attempts and a certified letter (or equivalent) as the final attempt.

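### Step 2.8 ends participation for a poor test-lens fit after the lens week is over, so lens-first subjects lose their spectacle period for no gain (minor)

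*Combined protocol and SAP*

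**What the plan says.** The interventional arm is a 2×2 crossover. Section 5.1: "Subjects will be randomly assigned to one of two sequences (Spectacle /ACUVUE OASYS 1-Day or ACUVUE OASYS 1-Day /Spectacle". A lens-first subject reaches Visit 2 at the end of the test-lens week. Step 2.8 then assesses fit, with the note that "if lens fit is unacceptable subject will be discontinued from the study". What follows for that subject involves no test lens:

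- Step 2.14: "The lenses will be removed by the subject".
- Step 2.21: "Subjects in the interventional arm will be scheduled for Visit 3 following a one-week washout period in which they will wear their habitual lens".
- Steps 3.14 and 3.15: at Visit 3 the subject goes into their own spectacles until Visit 4.

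Fit has already been checked before dispensing. Step 1.37 applies the same criteria, and step 1.40 makes continuation conditional: "The lens fit is acceptable OD and OS".

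Section 8.2 tells the investigator what to do for a discontinued subject, starting with "Complete the current visit (scheduled or unscheduled", and provides for replacement: "An additional subject will be enrolled if a subject discontinues from the study prematurely". The fit item in the 8.2 withdrawal list concerns subjects who could not be dispensed, so it neither requires nor overrides the Visit 2 rule. Step 2.21 does not override it either.

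**The concern.** At steps 1.37 and 3.21 the fit rule has an obvious purpose, because a lens is about to be sent home. At step 2.8 that purpose is gone for a lens-first subject. The only effect of discontinuing is to cancel Visits 3 and 4, and with them the spectacle NIBUT/NIKBUT. Section 4.2 chose the crossover precisely so that the treatment difference is measured within a subject, and here the pair is broken by design.

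The loss is not random. It depends on the performance of the test lens, and among follow-up fit failures it falls on one sequence only. A spectacle-first subject who fails at step 4.8 already has the spectacle reading, and under 8.2 gives the lens reading as well. Replacement and over-enrolment restore the number of pairs, but the replacements are again subjects whose fit stayed acceptable. The multiple-imputation sensitivity analysis in Section 14.9 depends on total dropout exceeding 15%, so it may not run and is not aimed at this loss. The Per-Protocol set in 14.3 requires all visits, so these subjects drop out of it.

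**Working it through.** **Inputs.** From Section 14.2: overall variance 34, correlation 0.5 for the same eye across periods, correlation 0.3 for the same subject across eyes and periods, true difference 2 s, two-sided 0.05, 40 subjects, stated power 86%. From Table 1: 46 randomised in the interventional arm (23 + 23) for 40 completers. Assumed, because the documents give no figure: equal sequence sizes, a Visit 2 fit-failure rate f of 2% to 10%, and a lens reading 2 s lower in poorly fitted subjects.

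**Variance components.** Subject 0.3 × 34 = 10.2; eye within subject 0.2 × 34 = 6.8; residual 0.5 × 34 = 17. Averaging two eyes gives a between-subject variance of 10.2 + 6.8/2 = 13.6 and a residual of 17/2 = 8.5 per period. The total per period mean is 22.1, and a within-subject period difference has variance 2 × 8.5 = 17.

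**Reproducing the plan.** With treatment, period and sequence in the model, the treatment variance is ¼(17/n₁ + 17/n₂). For 20 + 20 this is ¼(0.85 + 0.85) = 0.425, so SE = 0.652. A t-test with 2n − 2 = 78 df (n = complete pairs) gives power 0.858, matching the stated 86%.

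**Number exposed and lost.** 46/2 = 23 lens-first subjects. 23 × 0.02 = 0.46 and 23 × 0.10 = 2.3 spectacle periods.

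**Power when k lens-first subjects keep only the lens reading.** Let b = 13.6/22.1 = 0.615. The mixed model recovers part of the lost information, and the lens-first term 17/n₁ becomes (1 − b)² × 22.1/n₁ + (1 − b²) × 22.1/(n₁ − k) = 3.27/n₁ + 13.73/(n₁ − k). For n₁ = n₂ = 20 and k = 1: ¼(3.27/20 + 13.73/19 + 0.85) = 0.434, so SE = 0.659.

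| Randomised (lens-first + spectacle-first) | Spectacle periods lost | SE (s) | Power |
|---|---|---|---|
| 20 + 20 | 0 | 0.652 | 0.858 |
| 20 + 20 | 1 | 0.659 | 0.850 |
| 20 + 20 | 2 | 0.666 | 0.842 |
| 23 + 23 | 0 | 0.608 | 0.902 |
| 23 + 23 | 1 | 0.613 | 0.897 |
| 23 + 23 | 2 | 0.619 | 0.891 |
| 23 + 23 | 3 | 0.626 | 0.885 |

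**Shift in the estimate against full follow-up.** The treatment estimate is half the sum of the two sequence-specific lens-minus-spectacle differences, and only the lens-first one is affected.

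- Complete pairs only: ½ × f × 2 s = 0.020 s (f = 2%), 0.050 s (5%), 0.100 s (10%).
- Lens-only subjects kept in the mixed model: ½ × b × f × 2 s = 0.012, 0.031, 0.062 s.

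Against an SE of 0.608 this runs from 0.012/0.608 = 2% to 0.100/0.608 = 16%. Under the assumed direction, the shift favours the lens.

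**The 14.9 trigger.** If the interventional arm is the denominator, the planned dropout is 6/46 = 13.0%, below the threshold; one more gives 7/46 = 15.2%, above it.

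**The case against.** The best case against is that this does not matter much. The study is a pilot with exploratory hypotheses (2.3), and its sample size was not derived from a calculation (14.2). From the planned 46, power stays above the stated 86% even after three losses. Both the failure rate and the 2 s differential are assumptions, and nothing in the documents links fit to tear break-up time. The lens reading is kept, Section 14.1 uses available data, and a mixed model with the ITT set points to the smaller of the two shift ranges. All of that stands, and it is why the point is minor.

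A second argument is that the fix leaves other fit-driven losses in place. Randomisation precedes the check at 1.37, so a lens-first failure there loses both periods. A spectacle-first failure at 3.21 loses the lens period. This is true, and those losses may well be larger because fit has not yet been screened. But those rules stop a poorly fitting lens from being worn, which step 2.8 does not.

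A third is that acceptable fit is a uniform condition of participation, so the plan is simply choosing its population. That does not hold. A spectacle-first subject with an unacceptable fit at 4.8 contributes both readings, so the condition is not applied evenly across sequences.

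**Conclusion.** The concern holds and is minor. Step 2.8 gives up the spectacle half of a lens-first subject's pair without preventing any test-lens wear, and nothing in the plan exempts such a subject. The expected loss is 0.5 to 2.3 spectacle periods, with the low end more likely because these subjects passed the same fit criteria at dispensing. Power falls by about 0.8 points per unreplaced loss from 40 pairs, and over-enrolment more than covers that. The estimate would move by 0.01 to 0.06 s if lens-only subjects stay in the model, or 0.02 to 0.10 s with complete pairs. Section 14.5 names no analysis population, so which range applies is not settled. These sizes rest on the Section 14.2 variance assumptions, equal sequences, and the assumed failure rate and 2 s differential. The study's conclusion is not threatened.

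**What to change.** At step 2.8, replace the discontinuation note with: *Record the fit grade, complete all remaining steps of the visit, and continue to washout and Visit 3; unacceptable fit alone does not end participation.* Leave the adverse-event rules and investigator judgement as they are, and keep the existing note at 1.37 and 3.21, where a lens is about to be dispensed. Per-Protocol inclusion remains with the trial cohort review committee (14.3). Step 4.8 can be reworded to match, although it costs no primary data when 8.2 is followed.

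The cost is one sentence (two with 4.8), submitted to the IEC/IRB as a protocol amendment. Visits 3 and 4 are already scheduled, so no procedure and no test-lens exposure is added.

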7.3. Unscheduled Visits

If, during the investigation, a subject requires an unscheduled visit to the clinical site, the following information will be collected as applicable:

- Chief complaint prompting the visit. If the reason is an adverse event, the applicable eCRF for the adverse event must be completed and subject record completed as appropriate
- Date and time of the visit and all procedures completed at the unscheduled visit
- Review of adverse event and concomitant medications
- Documentation of any test article dispensed or collected from the subject, if applicable
- Slit lamp findings (using the Slit Lamp Classification Scale)

If the Investigator withdraws a subject from the study, the final study visit case report forms must be completed indicating the reason(s) why the subject was withdrawn. The subject record must be completed documenting the date and primary reason for withdrawal and the study CRA notified.

Any ocular and non-ocular Adverse Events that are ongoing at the time of the study visit will be followed by the Investigator, within licensure, until they have resolved, returned to pre-treatment status, stabilized, or been satisfactorily explained. If further treatment i.e., beyond licensure is required, the subject will be referred to the appropriate health care provider.

The following information will be collected during an unscheduled visit, as applicable.

| Unscheduled Visit | | | |
|-------------------|---|--|--|
| Step | Procedure | Details | |
| U.1 | Chief Complaints | Record the subject's chief complaints for reasons for the unscheduled visit. | |
| U.2 | Adverse Events and Concomitant Medications Review | Review any changes to the subject's medical history or concomitant medications from the previous study visit. Record any changes, and any adverse events. | |
| U.3 | Entrance VA | Record the entrance distance visual acuity (OD, OS) to the nearest letter. | |
| U.4 | Subjective Sphero-cylindrical Refraction | Perform bare-eye subjective sphero-cylindrical refraction with a phoropter and record the best corrected distance visual acuity to the nearest letter (OD, OS). | |
| U.5 | Slit Lamp Biomicroscopy | FDA Slit Lamp Classification Scale will be used to grade the findings. If the clearance of the fluorescein needs to be expedited, preservative-free rewetting drops may be | |

| Unscheduled Visit | | |
|-------------------|----------------------------|--|
| Step | Procedure | Details |
| | | instilled. |
| U.6 | Dispensing (if applicable) | Dispenses lenses as needed |
| U.7 | Exit Visual Acuity | Record the subject's exit distance visual acuity (OD, OS) to the nearest letter. |

7.4. Laboratory Procedures

Ex-vivo lenses will only be collected from the internal clinic site by the sponsor for potential analysis, under a separate protocol and/or reporting.

8. SUBJECTS COMPLETION/WITHDRAWAL

8.1. Completion Criteria

Subjects are considered to have completed the study if they:

- Provided informed consent
- Are eligible
- Completed all study visits

8.2. Withdrawal/Discontinuation from the Study

A subject will be withdrawn from the study for any of the following reasons:

- Subject death during the study period
- Subject withdrawal of consent
- Subject not compliant to protocol
- Subject lost to follow-up
- Subject no longer meets eligibility criteria (e.g. the subject becomes pregnant)
- Subject develops significant or serious adverse events causing discontinuation of study lens wear
- Subjects who have experienced a Corneal Infiltrative Event (CIE)
- Investigator's clinical judgment regarding the subject safety reasons (that it is in the best interest of the subject to stop treatment)
- Subject missed study visits
- Subject not compliant with study lens wear schedule
- Subject not successfully dispensed due to lack of efficacy and safety including poor vision, poor comfort or unacceptable fit

For discontinued subjects, the Investigator will:

- Complete the current visit (scheduled or unscheduled)
- Complete the Final Evaluation, indicating the reason that the subject was discontinued from the study
- Record the spherocylindrical refraction with best corrected distance visual acuity

- Collect used test article(s) (worn or brought to the visit) from the subject and discard them, unless otherwise stated in Section 7.2
- Collect all unused test article(s) from the subject

An additional subject will be enrolled if a subject discontinues from the study prematurely.

In cases where a subject is lost to follow-up, every possible effort must be made to contact the subject and determine the reason for discontinuation/withdrawal. The measures taken to follow up must be documented including two written attempts and a certified letter (or equivalent) as the final attempt.

9. PRE-STUDY AND CONCOMITANT INTERVENTION/MEDICATION

Concomitant medications will be documented during screening and updated during the study. Disallowed medications for this study include: Restasis, Xiidra, ocular steroids, or any medication (RX or OTC) that may interfere with contact lens wear (at the discretion of the investigator)

Concomitant therapies that are disallowed include: NA.

